#### Confidentiality Statement

---

The confidential information in this document is provided to you as an investigator or consultant for review by you, your staff, and the applicable Institutional Review Board. Your acceptance of this document constitutes agreement that you will not disclose the information contained herein to others without written authorization from the sponsor.

A central laboratory will be used in this study. All details regarding the collection, shipment of samples, reporting of results and alerting extreme values will be provided by the central laboratory and compiled in a Laboratory Manual.

#### 8.5.3 Vital signs

The following vital signs assessments should be performed at Screening, Baseline, and at all visits (including early discontinuation):

- Height- at screening visit only
- Weight
- Body temperature
- Respiratory rate
- Heart rate
- Blood pressure (sitting after 5 minutes on assessment visits, Supine after five minutes on treatment visits).

#### 8.5.4 Physical examination

Information collected during the physical examination will be recorded in the source documentation and subsequently on the Case Report Forms (CRF).

#### 8.5.5 Electrocardiogram

A 12-lead EKG will be performed and documented in the patient's medical chart at screening to ensure the patients does not have any contraindications for participation in the study. The investigator will review the ECG for eligibility criteria and sign/date the ECG report.

## 9. SAFETY ASSESSMENTS

Safety will be monitored throughout the trial as follows: monitoring and recording of anticipated adverse effects, unanticipated adverse effects (UAEs), serious adverse effects, unanticipated adverse device effects (UADEs), the assessment of laboratory parameters, and vital sign measurements.

### 9.1 Adverse Events

An adverse event (AE) is any untoward medical occurrence experienced by a subject in conjunction with their participation in a clinical trial regardless of whether the event is related to the procedure or study device. An AE can be any unfavorable and unintended sign, symptom, or disease temporally associated with the use of an investigational device whether or not it is related to the investigational device. This includes any condition that is new in onset (not present prior to study treatment) or aggravated in severity or frequency from the baseline condition, any condition resulting from concurrent illness,

---

#### Confidentiality Statement

---

The confidential information in this document is provided to you as an investigator or consultant for review by you, your staff, and the applicable Institutional Review Board. Your acceptance of this document constitutes agreement that you will not disclose the information contained herein to others without written authorization from the sponsor.

reactions to concomitant medications, progression of disease states, and also includes abnormal lab test results if associated with clinical signs or symptoms judged by the investigator to be clinically significant.

All AEs that occur after the consent form is signed must be reported in the AE section of the CRF. Documentation for all AEs should contain the Adverse Event (medical condition), the date the AE started and if applicable, the stop date; the preliminary assessment of the relationship to study treatment; any action taken with regard to study treatment; the outcome of the event; whether the event was serious and if so, whether the event was anticipated or unanticipated; and whether treatment was required.

For purposes of this study, a Serious Adverse Event (SAE) is defined in accordance with ISO 14155-2011(en), Clinical Investigation of Medical Devices, as an adverse event that, in the view of the Investigator or the sponsor:

- Led to death
- Led to serious deterioration in the health of the subject that resulted in:
  - i. Inpatient hospitalization or prolong hospitalizations
  - ii. Life threatening illness or injury
  - iii. Permanent impairment of a body structure or a body function
  - iv. Medical/Surgical intervention to prevent one of the outcomes listed in line ii. or iii. above

The sponsor is using the above ISO-14155-2011(en) definition of a SAE as an extra safety precaution in this study since no definition of “serious adverse effect” exists in Federal regulations governing medical device clinical trials, 21 CFR Part 812, Investigational Device Exemptions.

An unanticipated adverse device effect (UADE) is defined, in 21 CFR Part 812.3(s) as any serious [“serious” as defined above and in ISO14155-2011(en)] adverse effect on health or safety, or any life-threatening problem or death caused by, or associated with, a device, if that effect, problem, or death was not previously identified in nature, severity, or degree of incidence in the protocol or investigational plan (e.g., Investigators Brochure, Product Labeling, Informed Consent Document etc.) or any other serious problem associated with a device that relates to the rights, safety or welfare of the subject. Unanticipated adverse device effects will be collected in an ongoing fashion during the study and will be entered into a separate safety database.

All adverse events that do not meet any of the criteria for SAEs or UADEs should be regarded as non-serious adverse events and/or an anticipated AE and will be documented, and subsequently reported, at least annually to the IRB and Sponsor.

---

#### Confidentiality Statement

---

The confidential information in this document is provided to you as an investigator or consultant for review by you, your staff, and the applicable Institutional Review Board. Your acceptance of this document constitutes agreement that you will not disclose the information contained herein to others without written authorization from the sponsor.

Progression of disease reflects lack of therapeutic efficacy and should not be treated as serious adverse events. However, other events or complications meeting the criteria for serious adverse events should be considered as a serious adverse event and should be reported to the IRB regardless of presumed relationship to the investigational treatment.

All subjects who have been exposed to study treatment will be evaluated for adverse effects. All adverse effects will be evaluated beginning with onset, and evaluation will continue until resolution or recovery is observed or until the Investigator determines that the participant's condition is stable, whichever is earlier. The Investigator will take all appropriate and necessary therapeutic measures required for resolution of the adverse effect. Any medication necessary for the treatment of an adverse effect must be recorded on the study Concomitant Medication form. If more than one distinct adverse effect occurs, each event will be recorded separately.

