#### 9.3.2 Reporting of Unanticipated (Serious) Adverse Device Effects, Serious Adverse Events, or Device Deficiencies

Device Deficiency (DD) is the inadequacy of an investigational medical device related to its identity, quality, durability, reliability, safety or performance with or without patient involvement. This may include malfunctions, misuse or use error, or inadequacy in the information supplied by the manufacturer.

All DDs, Serious Adverse Events (SAE), whether Anticipated or Unanticipated, which occur during the study, including death, must be reported in writing within 3 working days of the site becoming aware of the event.

The local site Investigator must provide information on the SAE in a written narrative form, with as much information as possible. This should include a copy of the completed study Serious Adverse Effect form, and any other diagnostic information that will assist the understanding of the event. In the case of hospitalization, the de-identified admission report and if possible, the discharge summary should be obtained and submitted to the pharmacovigilance team (MVS and KAI) via email. Significant new information on ongoing serious adverse events should be provided promptly.

---

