#### 9.4 **Emergency procedure for unblinding**

For this study, the subject and the psychometrician/designee will be blinded. Neither the Renew™ NCP-5 operator nor the PI will be blinded. The psychometrician/designee administering all cognitive tests should be blinded. There does not seem to be any reason that the subject or psychometrician will be unblinded in the event of a serious adverse event. Only the investigator, who is unblinded, will need to assess what intervention the subject may need or whether the subject can continue in the study.

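### Section 9.1 defines a serious adverse event by outcome, then excludes disease progression, so admissions and deaths put down to dementia get conflicting instructions and their class depends on an unblinded call

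*Protocol*

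**What the plan says.** Four parts of the protocol bear on this.

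- **Adverse event (AE) definition, section 9.1.** The list of what counts as an AE includes "progression of disease states, and also includes abnormal lab test results" when these are clinically significant. Progression is therefore an AE.
- **SAE definition, section 9.1.** An SAE is defined "as an adverse event that, in the view of the Investigator or the sponsor" led to death or to a serious deterioration in health. The listed results of such a deterioration start with "Inpatient hospitalization or prolong hospitalizations" and go on to life-threatening illness, permanent impairment, and intervention to prevent either of these. No cause is exempted. The protocol explains the choice: "The sponsor is using the above ISO-14155-2011(en) definition of a SAE as an extra safety precaution in this study".
- **Exclusion, later in section 9.1.** "Progression of disease reflects lack of therapeutic efficacy and should not be treated as serious adverse events". The next sentence limits this: "However, other events or complications meeting the criteria for serious adverse events should be considered as a serious adverse event", and such events go to the IRB whatever their presumed relationship to treatment.
- **Reporting and assessment.** Section 9.3.2 says that all SAEs "which occur during the study, including death, must be reported in writing within 3 working days", with a written narrative. Section 9.1 puts AEs that are neither SAEs nor unanticipated adverse device effects (UADEs) into a residual class, non-serious and/or anticipated, reported at least annually. Section 9.2 gives the initial assessment to the investigator or a medically qualified designee. Section 9.4 says: "Neither the Renew™ NCP-5 operator nor the PI will be blinded".

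**The concern.** A site that admits a subject for abrupt cognitive or behavioural worsening has two instructions. By outcome, the admission is an SAE. If the investigator calls it progression, it is not. The protocol does not define progression for this purpose and describes no blinded check of the call.

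Two things are at stake. The first is reporting: the label decides whether the sponsor receives a narrative within days or the event waits for a report due at least annually. The second is the comparison between arms. The course of the disease is what the device is meant to change, and the person choosing the label knows which arm the subject is in. If progression is invoked more readily in one arm, recorded SAE counts will differ with no true difference in outcomes, or a true difference will shrink. Safety is the first secondary objective in section 4, so this comparison will be read.

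The stated reason for the exclusion also settles by rule something the trial should leave open. Worsening is taken to reflect lack of efficacy, yet section 1.4 says that acute studies of external counterpulsation have not been done in MCI or AD.

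**Working it through.** No arithmetic applies. The protocol gives no rate of SAEs, hospitalizations, deaths or progression events, and has no figure to reproduce. The check is to run each kind of event through the rules in sections 9.1 and 9.3.2.

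| Event | Outcome-based SAE definition | Exclusion of progression | Result |
|---|---|---|---|
| Worsening test scores only, no listed outcome | Not an SAE | Not an SAE | No conflict |
| Another event or complication leading to admission or death | SAE | SAE (kept by the limiting sentence) | No conflict |
| Admission attributed to progression itself | SAE | Not an SAE | **Conflict** |
| Death attributed to progression itself | SAE | Not an SAE | **Conflict** |
| Unanticipated death or life-threatening problem associated with the device | SAE | Not addressed | Also a UADE; no loss |

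**Does the limiting sentence remove the conflict?** No. It restores events other than progression. Its provision that presumed relationship does not matter is attached to those other events, so progression stays excluded whatever it led to.

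**Does section 9.3.2 remove it?** Not on its wording. Its mention of death sits inside a rule about device deficiencies and SAEs. It sets the deadline for an event already classed as an SAE and does not make an event one. A site could still read it as requiring every death to be reported, which conflicts with the exclusion.

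**Where do the conflicting events go?** Under the exclusion they are AEs but not SAEs. Unless they qualify as UADEs, they fall into the residual class. They lose the 3-working-day report, the narrative and the SAE form.

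**Who decides?** The investigator or designee makes the initial assessment and the principal investigator is unblinded. The SAE definition also admits the sponsor's view, so the sponsor could upgrade an event. Section 9.1 names no step that would prompt this for an event entered as progression and not serious.

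**Why an exclusion was probably wanted.** One SAE criterion is permanent impairment of a body function. Ordinary decline in MCI or mild AD could be argued to meet it, and reporting every falling score as an SAE would be unhelpful. That need is met by excluding score decline alone. It does not require excluding admissions and deaths.

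**The case against.** The strongest reply is that the sentence only means that worsening of the disease is an efficacy outcome, while whatever complication causes an admission or death is still an SAE. That is a sensible reading and may be what was intended. The text does not say it, however, and a site following the words as written would exclude a progression admission. Two reasonable sites could act differently, and that alone is reason to reconcile the passages.

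A reader might go further than the documents allow, and on these points the reply stands:

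- *That the events disappear from the safety data.* They do not. Every AE goes on the CRF with its outcome, relationship and seriousness entry, and section 9.2 makes capture independent of any link to treatment. The safety endpoint in section 5.2.2 is adverse events, laboratory results and vital signs, not SAEs alone.
- *That a decline caused by the device escapes the UADE check.* The UADE definition names unanticipated deaths and life-threatening problems associated with the device, and other serious problems associated with it, separately from serious adverse effects. The exclusion does not mention UADEs.
- *That neurological worsening goes unexamined.* Cognition is the primary endpoint and is tested by blinded psychometricians. MMSE2, MOCA, NPI and MRI are repeated, and use of health resources is compared between arms.
- *That section 1.4 shows harm to cerebral flow.* It reports a hypothesis about healthy subjects, a net zero or small negative change in mean flow velocity. The same section describes increased cortical perfusion in six scanned patients with Alzheimer-type dementia and no adverse events in the ten treated.

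The SAP and the Manual of Procedures are not shown. SAE tables or a working definition of progression may sit there. But tables cannot supply narratives that sites were told not to write.

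**Conclusion.** The contradiction within section 9.1 is real and should be corrected. Read literally, hospitalizations and deaths attributed to dementia progression are SAEs by definition and non-SAEs by instruction. An investigator who knows the arm decides which, so SAE counts by arm can be moved by labelling.

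The size cannot be estimated. It depends on how many admissions and deaths occur in this MCI and mild AD population, what share could plausibly be called progression, and how far that share differs between arms. The protocol gives none of these, so any numerical example would rest wholly on assumption. The direction is open too, since labelling could create or hide a difference.

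The conclusion concerns the SAE class and expedited reporting only. It rests on the literal reading of the exclusion and on there being no clarifying definition in documents that are not shown. It does not extend to loss of events from the AE data or to UADE reporting, neither of which the text supports.

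**What to change.** Reconcile the AE definition, the SAE definition and the exclusion in section 9.1 with the reporting rule in section 9.3.2:

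1. Replace the exclusion with a statement that any event meeting one of the outcome criteria in section 9.1 is recorded and reported as an SAE, whatever its presumed cause.
2. State that worsening on cognitive, functional or behavioural scores alone, without such an outcome, is not an SAE. This keeps the useful purpose of the present sentence.
3. Add a disease-progression flag to the AE and SAE case report form, so that the investigator's view of cause is kept without deciding whether the event is reported.
4. In the safety tables, show SAEs by arm with and without flagged events, and treat the table that includes them as the main one.

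The cost is one replaced sentence with its clarification, one CRF field and one extra table. The downside is a modest rise in SAE forms, many of them for events expected in this disease. No treatment or stopping rule is touched.

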## 9.2 Adverse Event Assessment

All adverse events (AE), observed or reported, will be initially assessed by the Investigator or his/her medically qualified designee, and recorded on the study Adverse Effect Form according to the protocol and the Manual of Procedures. The need to capture AEs is not dependent upon whether or not the clinical event is associated with the use of the study treatment.

Severity will be assessed using the following definitions:

- Mild: Aware of sign or symptom, but easily tolerated
- Moderate: Discomfort sufficient to cause interference with usual activity
- Severe: Incapacitating, with inability to work or do usual activity

The relationship to Investigational Treatment will be assessed by the Investigator using the following criteria:

- Not Related Evidence exists that the adverse event definitely has a cause other than the study treatment (e.g. pre-existing condition or underlying disease, intercurrent illness, or concomitant medication) and does not meet any other criteria listed.
- Suspected There is a reasonable possibility that the treatment caused the adverse event. "Reasonable possibility" means there is evidence to suggest a causal relationship between the treatment and the adverse event. A causal relationship requires a temporal relationship to exist between the adverse event onset and administration of study treatment.

---

### Confidentiality Statement

---

The confidential information in this document is provided to you as an investigator or consultant for review by you, your staff, and the applicable Institutional Review Board. Your acceptance of this document constitutes agreement that you will not disclose the information contained herein to others without written authorization from the sponsor.

- **Probably Related** Strong evidence exists that the study treatment caused the adverse event. There is a temporal relationship between the event onset and administration of the study treatment. There is strong therapeutic evidence that the event was caused by the study treatment. The participant's clinical state and concomitant therapies have been ruled out as a cause.

All subjects who have been exposed to study treatment will be evaluated for adverse effects. All adverse effects will be evaluated beginning with onset, and evaluation will continue until resolution or recovery is observed or until the Investigator determines that the participant's condition is stable, whichever is earlier. The Investigator will take all appropriate and necessary therapeutic measures required for resolution of the adverse effect. Any medication necessary for the treatment of an adverse effect must be recorded on the study Concomitant Medication form. If more than one distinct adverse effect occurs, each event will be recorded separately.

### 9.3 Adverse Event Reporting

#### 9.3.1 Adverse Event Reporting

The study period during which adverse events must be reported is defined as the period from signing informed consent to the end of the study treatment follow-up (Month 12). If an adverse event is unresolved by the day of the 12-month data collection visit, and it is possible to follow the participant thereafter, this will be attempted for 30 days after the participant's last study treatment.

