Subjects, ages 55-85, will be consented for 13 months study participation, and will receive thirty-five 60-minute Renew™ NCP-5 treatment sessions during a 7-to-12-week initial treatment period, and then transition to a lower frequency maintenance period (twice a week) for a total treatment period of 24 weeks. During the initial treatment period (~1-12 weeks) subjects should be treated five days per week but at a minimum receive treatments three days per week. For subjects who are unable to complete 5 treatment days per week, the treatments should be spread-out as much as possible. In order to complete 5 treatments per week, it is permissible for those subjects to have 2 treatments per day as long as there are no more than 3 days between treatments. If two treatments are conducted on the same day, subjects will need to wait a minimum of one-hour between treatments. Treatments should be completed per the above schedule. The schedule may be adjusted due to holidays or extenuating circumstances. If subjects need to miss visits during any particular week, then treatments should be added to the week prior to or after the missed visits. A total of 35 treatments must be completed within the 12-week period. More than 7 days between treatments would be considered a protocol violation.

Once the first 35 treatments have been administered, subjects will start the maintenance period. During the maintenance period, subjects should be treated two days per week, one session per day with a minimum of two full days between each treatment. Subjects may be rescheduled on an as needed basis as long as 6 treatments are maintained within a 3-week period. Rescheduling should be kept to a minimum and all efforts should be made to have treatments every week.

Assessment visits should occur the day following the last treatment session but no later than 2 days (48 hours) after the last treatment. If necessary, on an as-needed basis, a treatment session of 30 minutes or more ( $\geq 30$  minutes) will be considered as a completed session.

---

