#### Confidentiality Statement

---

The confidential information in this document is provided to you as an investigator or consultant for review by you, your staff, and the applicable Institutional Review Board. Your acceptance of this document constitutes agreement that you will not disclose the information contained herein to others without written authorization from the sponsor.

Subjects are free to withdraw consent and discontinue participation at any time. Their decision to do so will not affect their ability to receive medical care or lose any benefits to which they are otherwise entitled.

All withdrawn subjects will be encouraged to complete study assessments at 6, 12, 18, 24 weeks, 9 and 12 months/end of study assessments and final MRI. Safety follow up procedures to capture adverse events, SAE or unanticipated problems will be initiated.

If the study is temporarily suspended or terminated early, written notification documenting the reason for study suspension or termination will be provided by the terminating party. The PI will inform the IRB and sponsor and provide the reason for termination or suspension. Determination of unexpected or significant risks to subjects, demonstration of efficacy, insufficient compliance to protocol requirements, determination of futility or incomplete data are some of the potential reasons for termination or suspension of the study. Enrolled subjects will be followed up to week 24 if the trial is terminated early.

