## 7.6 Duration of Therapy

Subjects will receive thirty-five 60-minute Renew™ NCP-5 sessions during the 7-to-12-week initial treatment period, and then transition to a lower frequency maintenance period (twice a week) for a total treatment period of 24 weeks.

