### 8.3 Study Schedule

**Table 1: Renew™ NCP-5 Treatment Schedule**

Treatment Schedule	
Renew™ NCP-5 initial treatment visits	3-5 treatments per week to 35 treatments
Renew™ NCP-5 maintenance treatments	2 treatments per week as maintenance up to week 24

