8.4.11 Week 24 – Day 168 (+/- 2 days)

- Cognitive assessments: It is recommended that subjects come in the day following treatment for all assessment testing but no later than 2 days (48 hours) post last treatment. Administer cognitive assessments including:
  - vADAS-Cog (must be administered first and before 3:00 PM; should be administered at the same time of day)
  - ADCS-CGIC
  - ADCS-ADL
  - Trail Making A & B
  - Logical Memory I & II
- MOCA
- Vital signs (If non-treatment day)
- Hachinski
- MMSE2
- TUG Test
- Functional Reach Test
- Health Resource Utilization Survey - RUI
- NPI
- Exercise regimen
- Patient questionnaire

---

Confidentiality Statement

---

The confidential information in this document is provided to you as an investigator or consultant for review by you, your staff, and the applicable Institutional Review Board. Your acceptance of this document constitutes agreement that you will not disclose the information contained herein to others without written authorization from the sponsor.

- Review concomitant medications and treatments
- Collect adverse events
- If treatment occurs on same day as assessments administer the treatment first
  - Vitals (Pre & Post)
  - Administer two treatments per week separated by at least 2 days as maintenance up to 24 weeks
- Draw blood for:
  - Blood lipid panel, CBC, fibrinogen, CRP, LP-PLA2, MPO, lipoprotein particles to include: LDL-P, Lp(a)-P, VLDL-P, IDL-P, ApoB, B12, TSH
  - Blood viscosity
- MRI (Must be done after last treatment but may take place on or before the Week 24 Assessment Visit)

For sites collecting data for exploratory endpoints, complete the following assessments:

- Ultrasound: Transcranial Doppler; cerebral artery blood flow
- Moor deep tissue oxygenation

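### Section 9.3.1 counts the 30-day follow-up of adverse events open at month 12 from the last treatment, so for completers the window closes about 167 days before the visit that triggers it

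*Protocol*

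**What the plan says.** Section 9.3.1 of the protocol sets the adverse event reporting period from consent to month 12. It then adds a rule for events still open at the end. The trigger is "If an adverse event is unresolved by the day of the 12-month data collection visit", with the condition "and it is possible to follow the participant thereafter". The length and starting point are given as "this will be attempted for 30 days after the participant's last study treatment".

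The schedule fixes when treatment stops. Section 7.6 describes an initial phase and then maintenance "for a total treatment period of 24 weeks". Table 1 in section 8.3 has "2 treatments per week as maintenance up to week 24". Table 2 shows no device treatment at month 9 or month 12. The week 24 visit is on Day 168 (+/- 2 days, section 8.4.11) and the month 12 visit on Day 365 (+/- 7 days, section 8.4.13), with Day 1 as the first treatment day.

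Two other places bear on the point. Sections 9.1 and 9.2 each continue evaluation of an adverse effect until it resolves, the participant recovers, or the investigator judges the condition stable, whichever comes first, with no day limit. Section 9.3.2 asks for prompt updates on ongoing serious events.

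**The concern.** The sentence is triggered at one event and timed from another. Its trigger and its use of a word meaning after that visit both point to follow-up beyond month 12. Its clock starts when treatment ends, about six months earlier. A 30-day period cannot bridge that distance, so for a participant treated through week 24 it has expired before the question of an open event at month 12 can arise.

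Safety is a secondary objective (section 4) and is listed among the secondary endpoints (section 5.2.2). Section 9.1 asks for an outcome and, where applicable, a stop date for every adverse event. This is the only provision addressed specifically to events open at the last scheduled visit, and it has no effect for the ordinary completer.

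**Working it through.** The protocol gives a length and an anchor but no end day, so there is no stated figure to reproduce. The check is day arithmetic.

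**Inputs**
- End of treatment: week 24, 24 × 7 = Day 168 (sections 7.6 and 8.3).
- Week 24 visit: Day 166 to 170 (section 8.4.11).
- Interval from last treatment to assessment: section 5.1 says "Assessment visits should occur the day following the last treatment session but no later than 2 days (48 hours) after the last treatment". Section 7.5 also allows assessment on the treatment day, after treatment. The interval is therefore 0 to 2 days.
- Month 12 visit: Day 358 to 372 (section 8.4.13).
- Follow-up window: 30 days from the last treatment (section 9.3.1).

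**Nominal case**
- Window end = 168 + 30 = Day 198.
- Gap to the triggering visit = 365 − 198 = 167 days.

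**Range with on-schedule visits and the 48-hour rule**
- Earliest last treatment = 166 − 2 = Day 164; window ends 164 + 30 = Day 194.
- Latest last treatment = 170 − 0 = Day 170; window ends 170 + 30 = Day 200.
- Smallest gap = 358 − 200 = 158 days.
- Largest gap = 372 − 194 = 178 days.

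These are not hard limits. Section 5.1 words the 48-hour rule as something that should happen, and section 8.4.11 has "It is recommended that subjects come in the day following treatment for all assessment testing".

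**Does the conclusion depend on that rule?** No. For the window to reach even the earliest permitted month 12 visit, the last treatment would have to fall on 358 − 30 = Day 328 or later, which is 328 − 168 = 160 days after treatment is scheduled to stop. A participant who stops treatment early but attends month 12 has a window that ends sooner still.

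**If the 30 days ran from the 12-month visit**
- Nominal end = 365 + 30 = Day 395.
- Range = 358 + 30 = Day 388 to 372 + 30 = Day 402.

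**Against the participation period.** Sections 5.1 and 6.3 give 13 months, which is about 13 × 365/12 = 395 days. Counting up to 28 days of screening (section 6.3), Day 395 is 395 + 28 = 423 days after screening starts. Counting from Day −35 (Table 2), it is 395 + 35 = 430 days. Both are about 14 months.

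**The case against.** The strongest reply is that little is lost. Sections 9.1 and 9.2 both state the duty to evaluate until resolution, recovery or stability, and neither sets a day limit. Section 9.3.2 keeps serious events current. Section 9.3.1 speaks of an attempt; it does not say that evaluation stops after 30 days or that longer follow-up is barred. A best-effort contact rule under reporting can coexist with the evaluation duty. This stands, and it keeps the point minor.

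A reader might infer more: that 9.3.1 caps follow-up and so contradicts 9.1 and 9.2, or that sites are left with no usable rule for events still open and unstable. The documents do not support that. The wording sets no cap, and 9.1 and 9.2 are a usable rule. Whether outcomes or stop dates would in practice be recorded inconsistently depends also on the Manual of Procedures and the CRF Completion Guidelines, which are not at hand.

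A reader might also try to rescue the anchor through early termination of the trial. Section 6.4 says "Enrolled subjects will be followed up to week 24 if the trial is terminated early", which would put the last visit close to the last treatment. But the trigger in 9.3.1 names the 12-month visit, and 6.4 does not say that treatment continues to week 24 after the trial is stopped. The individual early termination visit has more textual support, since section 8.4.14 and Table 2 give it the 12-month procedures. It is still not the completer's path. Nor does the active-treatment study offered to sham participants after month 12 (section 8.4.15) help: it is a separate study and does not move the last treatment in this one.

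**Conclusion.** The point holds as a wrong anchor in one clause. For participants treated through week 24, the window closes at about Day 198, nominally 167 days before the visit that triggers it (158 to 178 days on schedule), and the clause provides no follow-up after month 12. The nominal figure assumes that the last treatment is at the end of week 24 and that the month 12 visit is on Day 365. The range assumes that the visit windows and the 48-hour rule are kept.

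Severity is minor. Reporting from consent to month 12, the evaluation duty in 9.1 and 9.2, serious-event updates and the efficacy analysis are unaffected. Events judged stable by month 12 raise no question, because 9.1 and 9.2 end there. The protocol gives no count of events likely to be open and unstable at month 12, so the number of participants concerned cannot be stated.

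**What to change.** In section 9.3.1, replace the last-treatment anchor with *after the 12-month (or final) visit*, and state that this is a minimum attempt that does not limit the evaluation required by 9.1 and 9.2. Leave 9.1 and 9.2 as they are.

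The cost is an amendment of one sentence, which needs IRB approval unless it is classed as administrative (section 17.1), and a few extra contacts for participants whose events are still open and not stable. Because the new window runs past the 13-month participation period, sections 5.1 and 6.3 and the consent wording should be checked, and aligned if needed, so that contact up to about 14 months after screening starts is covered. No visit, endpoint or analysis changes.
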